## **Study Design and Methods**

### **I. Subjects:**

#### **A. Overview:**

The proposed study will comprise of two parts: Part I: an observational study based on ecological momentary assessment, and Part II: a randomized partial crossover clinical trial. Same subjects will participate in both parts of the study.

In the observational study, the dietary intake of the subjects will be evaluated using an ecological momentary assessment approach for 7 days. In the randomized partial crossover clinical trial, four test breakfasts will be administered so that each subject will get exposed to only two out of the four diets (thus, partial crossover). Therefore, there will be six possible combinations of diets (i.e.  $4! / 2! [4-2]!$ ) and 12 possible ordered combinations (i.e. permutations;  $4! / [4-2]!$ ) of diets. Four subjects will be randomly assigned to each of these 12 possible ordered combinations of diets. Thus, the total sample size will be 48 (i.e.  $n = 4 \times 12$ ).

#### **B. Recruitment:**

Advertisements for the recruitment of participants will be posted on social media and notice boards within the Texas Tech University (TTU) including the web-based notice boards (Tech Announce), radio and television. Appendix A-1 and Appendix A-2 provide written material and Flyer Ad that would be used for these announcements. No students of any investigators will be recruited or enrolled for this study and flyer ads or person-to-person solicitation scripts will not

be administered in any of the investigator's classrooms. The flyer ad described in Appendix A-2 will be posted and displayed on and around Texas Tech University campus on all appropriately designated signage areas when permission to do so has been granted by the proper authority. The flyer will be designed to have tear-off contact information tabs for all participants interested in the study.

*Inclusion criteria:*

- 48 non-diabetic individuals (fasting glucose  $< 126$  mg/dL)
- male or female
- $BMI \geq 20$  and  $\leq 60$  kg/m^2
- Age: 18 – 65 years

*Exclusion criteria:*

- Diabetes
- On antidiabetic medication
- Pregnant or lactating females
- Having a history of gestational diabetes
- Having an unstable cardiac condition
- Having a major systemic illness
- Having a history of drug abuse
- Having a history of eating disorders
- Having uncontrolled hypothyroidism
- Having familial hyperlipidemias
- Having allergies sensitivity to or dislike of eggs
- Consumption of  $< 1$  egg per week
- Attempting to lose weight
- On medications that may influence or inhibit appetite, sensory functioning, or hormone signaling- e.g. antibiotics, anti-depressants, obesity medications. Weight loss  $> 5\%$  in the past 3 months.

**II. Procedures:**

**A. Initial work**

Individuals who express an interest in participating will be contacted by a graduate research assistant who will administer a structured telephone interview (Appendix B) to 1) provide information related to the requirements of the study, along with potential risks and benefits 2) Screen for eligibility based on specific inclusion and exclusion criteria. All potential subjects will be informed that their responses will remain confidential and that taking part in the screening interview in no way obligates them to participate.

Potential participants who meet participation criteria as assessed via the telephone prescreening process will be contacted by the study team via email/phone within 48 hours following the interview to inform of eligibility (or ineligibility) and to schedule an initial visit if deemed eligible.

### **B. Anthropometric Measurements and Blood Pressure**

Height and weight will be measured using a wall-mounted stadiometer and standardized scale, respectively. BMI (body mass index) will be calculated from the measured height and weight using the formula weight (kg)/height (m^2). Waist and hip circumference will be measured according to the World Health Organization's methods for measuring waist and hip circumference . Blood pressure will be measured using a standardized electronic sphygmomanometer.

### **C. Remote Food Photography Method (RFPM)**

RFPM was developed and validated by our co-investigator (CM). RFPM employs smartphone technology as a means of estimating energy intake remotely from participants' home environments. Collection of RFPM data will be done using the SmartIntake© smartphone "app". Subjects will be trained to take photos of foods before eating and of the leftovers, if any. Subjects can use their own phone or a smartphone will be provided with the app. The photographs will be sent to co-investigator (CM), where they will analyze the RFPM data (food images) in coordination with the collaborators on the project and quantify energy and macronutrient intake. These data will be sent back.

### **D. Test Meals**

Four test breakfasts will be matched for energy density, and macronutrient composition (Table 1). Breakfasts will be prepared and assembled onsite at Texas Tech University. Preparing and serving meals will be done in accordance with standardized measures and in compliance with food safety regulations.

Table 1. Macronutrient Composition of Test Breakfasts

	Test Breakfast A-Egg Breakfast	Test Breakfast B- Egg Breakfast with High Saturated Fat	Test breakfast C- Cereal Breakfast	Test Breakfast D-Cereal Breakfast with High Saturated Fat
Energy (kcal)	438	450	447.48	449.6
Protein (g)	22.6	23.4	21.41	22.56
Fat (g)	22.61	24.91	19.55	22
Saturated Fat (g)	5.193	10.893	2.916	10.616
Carbohydrates (g)	44.37	40.45	48.741	41.8
Fiber (g)	10	11.5	7.427	5.667
Glycemic Index	37.48	35.98	55.54	51.52
Glycemic Load	16.63	14.55	27.07	21.53
Weight (g)	328	310	387	352
Energy density (kcal/g)	1.34	1.45	1.17	1.28

Table 2. Contents of Test Breakfasts

A-Egg Breakfast	B- Egg Breakfast with High Saturated Fat	C- Cereal Breakfast	D-Cereal Breakfast with High Saturated Fat
2 Scrambled Eggs	2 Scrambled Eggs	1c Special K RTE High Pro Cereal	1c Special K RTE High Pro Cereal
120 mL Skim Milk	120 mL 2% milk	200 mL Silk Original Soymilk	200 mL Silk Original Soymilk
2 Slices Nature's Own Double Fiber Wheat Bread	2 Slices Nature's Own Double Fiber Wheat Bread	1 Slice [name] Thin Bread	1/2 Slice Arnold Double Protein Whole Grain Bread
30g Margarine	15 g Butter	35g Margarine	15 g Butter
18g Smucker's Strawberry Jam	15g Smucker's Strawberry Jam	10 g Smucker's Sugar Free Strawberry Jam	

Table 3. Flow of Procedures

Group (n=4)	Visit 1	1-7 Days	Visit 2
-------------	---------	----------	---------

Height, weight, waist and hip circumference and blood pressure	x		
Test Breakfast 1 (Part II)	x		
Blood for HbA1c (Part II)	x		
Blood (glucose, insulin, GLP-1, PYY3-36, ghrelin) at 30 min before and 30, 60, 90, 120, 180, min. after breakfast (Part II)	x		x
Food frequency questionnaire (Part I)	x		
Satiety questionnaire at 30 min before and 30, 60, 90, 120, 180 min after breakfast (Part II)	x		x
RMR measurement at 30 min before and 60 and 120 min after breakfast (Part II)	x		
24-hour Recall (Part I)		D1	
Sending images of the pre-and leftovers of all meals including snacks (Part I)		x	
Test Breakfast 2 (Part II)			x

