**01-03-2018**

**Unique Protocol ID: IRB 2017-215**

**NCT03404700**

## **Summary**

Eggs are nutrient dense, convenient, affordable, and provide key macro and micronutrients in one's diet. Despite having a lot of benefits of consuming eggs in relation to health recent epidemiological studies raise health concerns about egg intake for subgroups of people. For instance, under free-living conditions, higher egg intake is associated with increased cardiovascular disease (CVD) risk in diabetic individuals as well as increased risk of developing type 2 diabetes. However, these studies do not establish that egg consumption "causes" health issues.

It is also possible that the association of egg intake with increased CVD risk in diabetics, or with a greater risk of developing diabetes, is simply due to the other foods that people usually eat with eggs, such as saturated fats, and not due to eggs *per se*.

For part I, the investigators propose to test this hypothesis by determining the food intake of 48 non-diabetic individuals under free-living conditions using the remote food photography method (RFPM), which uses smartphone technology. The frequency of egg consumption will be obtained using a food frequency questionnaire (FFQ). In addition, participants will record their food intake using food record diary and a 24-hour food recall method. Energy intake information gathered from RFPM will be compared with the 7-day food record and the 24-hour recall.

Next, for part II, the same study participants will be offered four separate test breakfasts of similar calories, containing 1) Eggs; 2) Eggs with a high amount of saturated fat; 3) Cereal breakfast (neither eggs nor saturated fat); or 4) Cereal breakfast with a high amount of saturated fat. Alteration of blood glucose, insulin, hunger, and satiety hormones (ghrelin, PYY, GLP-1), and metabolic rate will be measured before and after each breakfast in part II.

The investigators expect to determine if the purported association of eggs to alterations in glucose control and related metabolic alterations are independent of eggs, but mainly due to saturated fat is eaten along with eggs rather than the egg consumption itself.

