## **B. Hypotheses:**

These aims will test the following hypotheses:

1. Meals that include eggs will have higher energy and saturated fat contents as determined by RFPM, compared to corresponding meals (i.e. breakfast, lunch, or dinner) without eggs.
2. As determined by RFPM, individuals of the study sample who will be in the highest quartile in terms of egg consumption in the free-living condition (defined as high egg consumers) will have a higher intake of saturated fat and total energy as compared to individuals who will be in the lowest quartile in terms of egg consumption (defined as low egg consumers).
3. Baseline insulin level, blood glucose level, the Homeostatic Model Assessment (HOMA) index of insulin resistance using fasting glucose and insulin levels, and HbA1C will be positively associated with total EI and saturated fat intake determined by RFPM, even when adjusted for age, sex, BMI and waist circumference
4. Above outcome variables will not be associated with egg intake determined by RFPM.

5. In the randomized partial crossover study, presence of eggs in the breakfast will be associated with a) a greater increase (i.e. both area under the curve and pre-post change) in satiety hormones (i.e. PYY and GLP-1), b) a less profound increase in blood glucose and insulin levels, c) a greater decrease in the hunger hormone (ghrelin) and d) an increase in the area under the curve of metabolic rate when controlled for the content of saturated fat in the test diets.
6. In the randomized partial crossover study, presence of a high amount of saturated fat in the breakfast will be associated with a) a greater increase (i.e. both area under the curve and pre-post change) in satiety hormones (i.e. PYY and GLP-1), b) a less profound increase in blood glucose and insulin levels, c) a greater decrease in the hunger hormone (ghrelin) and d) an increase in the area under the curve of metabolic rate when controlled for the presence of eggs in the test diets.
7. In the randomized partial crossover study, the associations mentioned in hypothesis 5 will be moderated by the presence of a high amount of saturated fat in the diet.
8. Estimates of total EI by RFPM will be significantly greater than EI estimates by 7-day food record and the 24-hour recall in dietary assessment.

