### **C. Significance:**

An association between egg consumption and diabetes should not be ignored. However, it is important to identify if such an association does indeed exist and, if so, whether or not there is evidence that suggests that it is not the eggs themselves that drive the association, but rather a concurrent undesirable profile of macronutrient intake. Food intake data assessed by subjective recall methods are highly questionable due to potential inaccuracies . Capturing food intake data in real time by RFPM is the greatest strength of this project. The RFPM has been validated for accuracy against the doubly labeled water method . With high accuracy, we will identify the nutrients associated with egg consumption. Intake at every meal will be captured for 7 days in a free-living population, which eliminates the reporting bias around subjective measures of food intake and provides greater fidelity of reporting usual diet. This will help in better understanding the health effects that are currently ascribed to eggs by epidemiological studies using dietary recall methods. We expect that this study will demonstrate that intake of eggs is associated with an undesirable profile of macronutrient intake. By doing measuring blood

glucose, insulin levels following four tests breakfast that include eggs and saturated fats we will be able to measure the acute effects of egg based diet and influence of saturated fats to glycemic status. In addition, by doing hunger and satiety hormones will enable to explain the changes that coexist with insulin and glucose alterations. RMR will give indirect measurement of fed state. Overall, the studies will provide stronger evidence to accept or refute some of the adverse effects reportedly associated with egg consumption, so that appropriate dietary recommendations could be designed. It will form the basis for future research to determine if the dietary pattern accompanying eggs and not eggs per se is linked to diabetes and other adverse metabolic consequences.

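### The four breakfasts are said to be matched, but Table 1 shows only energy and protein are close; separately, the egg and saturated-fat terms can be read only as contrasts among whole breakfasts

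*Combined protocol and SAP*

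**What the plan says.** Section II.D, Test Meals, introduces Table 1 with the sentence "Four test breakfasts will be matched for energy density, and macronutrient composition (Table 1". The Summary promises less: "four separate test breakfasts of similar calories". Table 1 gives the composition of breakfasts A (egg), B (egg, high saturated fat), C (cereal) and D (cereal, high saturated fat). Table 2 gives their contents.

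The hypotheses are framed by ingredient. Hypothesis 5 says "presence of eggs in the breakfast will be associated with a) a greater increase" in satiety hormones and a smaller rise in glucose and insulin, "when controlled for the content of saturated fat in the test diets". Hypothesis 6 says "presence of a high amount of saturated fat in the breakfast will be associated with" the same pattern. Hypothesis 7 says "the associations mentioned in hypothesis 5 will be moderated by the presence of a high amount of saturated fat in the diet". The Significance section says "we will be able to measure the acute effects of egg based diet and influence of saturated fats to glycemic status". The Summary expects the alterations in glucose control to be "independent of eggs, but mainly due to saturated fat is eaten along with eggs rather than the egg consumption itself".

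The SAP models each Part II outcome on presence of eggs, presence of high saturated fat and their interaction. Its covariates are all at subject level, and it states no coding for the two indicators. Glucose and insulin AUC are primary outcomes 5 and 6.

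**The concern.** There are two issues, and they should be kept apart.

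First, a factual statement about the intervention disagrees with the table it cites.

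Second, the model terms are named after eggs and saturated fat, but each compares pairs of meals that also differ in other ways. Some of those differences, notably glycemic load, bear on glucose and insulin. If the terms are read as effects of the ingredient, Hypothesis 5b or 6b could appear confirmed because the meals carried different glycemic loads. An effect of saturated fat that the Summary expects could equally be masked.

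**Working it through.** **Inputs.** All are from Table 1. The last column is the largest value divided by the smallest.

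| | A | B | C | D | Max/min |
|---|---|---|---|---|---|
| Energy (kcal) | 438 | 450 | 447.48 | 449.6 | 1.03 |
| Protein (g) | 22.6 | 23.4 | 21.41 | 22.56 | 1.09 |
| Carbohydrate (g) | 44.37 | 40.45 | 48.741 | 41.8 | 1.20 |
| Energy density (kcal/g) | 1.34 | 1.45 | 1.17 | 1.28 | 1.24 |
| Fat (g) | 22.61 | 24.91 | 19.55 | 22 | 1.27 |
| Glycemic index | 37.48 | 35.98 | 55.54 | 51.52 | 1.54 |
| Glycemic load | 16.63 | 14.55 | 27.07 | 21.53 | 1.86 |
| Fiber (g) | 10 | 11.5 | 7.427 | 5.667 | 2.03 |
| Saturated fat (g) | 5.193 | 10.893 | 2.916 | 10.616 | differs by design |

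**Reproducing the table's derived rows.** Energy divided by weight (328, 310, 387, 352 g) gives 1.34, 1.45, 1.16 and 1.28; only C is off, by 0.01. Glycemic index × carbohydrate / 100 gives 16.63, 14.55, 27.07 and 21.54, which agrees within 0.01. The table is legible and internally consistent.

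**What was promised.** The sentence covers energy density and the macronutrients. Protein is close. Carbohydrate, energy density and fat differ by 20%, 24% and 27%.

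**What was not promised but also differs.**
- Egg versus cereal, glycemic load: (16.63 + 14.55)/2 = 15.59 against (27.07 + 21.53)/2 = 24.30, or −36%. By pair it is −38.6% (A vs C) and −32.4% (B vs D).
- Egg versus cereal, fiber: 10.75 against 6.55 g, or +64%.
- High versus low saturated fat, glycemic load: (14.55 + 21.53)/2 = 18.04 against (16.63 + 27.07)/2 = 21.85, or −17%. By pair it is −12.5% (B vs A) and −20.5% (D vs C).

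**Where the glycemic-load gaps come from.** For egg versus cereal, mean glycemic index is 36.73 against 53.53 (−31%) and mean carbohydrate 42.41 against 45.27 g (−6%). That gap is mostly glycemic index. For high versus low saturated fat, mean glycemic index is 43.75 against 46.51 (−6%) and mean carbohydrate 41.13 against 46.56 g (−12%). That gap is mostly carbohydrate, which was promised as matched. With carbohydrate minus fiber, the carbohydrate figures become −18% (31.66 against 38.72 g) and −14% (32.54 against 37.84 g). The ordering holds, but the exact split depends on the definition, so I give no shares.

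**Saturated fat itself.** The yes/no indicator treats A (5.193 g) and C (2.916 g) as the same level. The step is 10.893 − 5.193 = 5.7 g with eggs and 10.616 − 2.916 = 7.7 g with cereal. Hypothesis 5 is therefore not controlled for saturated-fat content, and Hypothesis 7 compares unequal steps.

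**What the model can separate.** Four fixed breakfasts give 4 − 1 = 3 degrees of freedom between meals. Eggs, saturated fat and the interaction use all three. Intercept plus these terms has rank 4; adding any Table 1 nutrient leaves the rank at 4. No meal-composition covariate is estimable.

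**Coding.** With indicators at +1/2 and −1/2 the terms are (A+B)/2 − (C+D)/2, (B+D)/2 − (A+C)/2 and (B−A) − (D−C). With 0/1 coding and C as reference, the two main terms are instead A−C and D−C; with A as reference they are C−A and B−A. The interaction test is the same either way, but the meaning of the main terms is not.

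**The case against.** The strongest reply is that whole foods cannot be exchanged at equal energy without other constituents moving, that Table 1 discloses every difference, and that no tolerance for matching is stated. Aims 2, 3 and 5 and the Part II breakfast outcomes already compare named breakfasts. The hypotheses speak of association, and the phrase about an egg-based diet in the Significance section can be read as a meal.

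Much of this stands. Some co-variation is unavoidable, and the weaker claim of similar calories is supported. It does not rescue the matching sentence: energy and protein vary by 3% and 9%, and the next smallest spread among the promised items is 20%. Nor does it cover the wording by ingredient in Hypotheses 5 to 7, or the Summary's expectation, which is the clearest attribution.

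A reader might infer that the attribution problem is caused by the broken matching promise. For the egg term it largely is not: most of that gap is glycemic index, which nobody promised to match, and the rank argument would hold for any four fixed meals. The link is real mainly for saturated fat, through carbohydrate.

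A reader might also take every menu change in Table 2 to be surplus to the saturated-fat swap. The table does not show that: the bread is the same in A and B, and the soymilk is the same in C and D.

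**Conclusion.** The matching sentence is wrong as written. Carbohydrate, energy density and fat differ by ratios of 1.20, 1.24 and 1.27. As a separate matter, the SAP's egg and saturated-fat terms are contrasts among breakfasts that carry glycemic-load gaps of −36% and −17%, and the design leaves nothing with which to separate these from the named ingredient.

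Both gaps run in the direction that Hypotheses 5b and 6b predict for glucose and insulin. The second runs against the Summary's expectation about saturated fat. The glycemic-load argument concerns those two outcomes; the limit on attribution applies to every outcome fitted with this model.

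It would be tempting to conclude that the trial is invalid or that the glucose and insulin results are biased by a known amount. The documents support neither. Randomization protects the comparison of breakfasts as served. No relation between meal composition and response is given, so the size of any distortion cannot be stated, and no direction is shown for the interaction.

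The assumptions are that Table 1 describes the meals as served and that close means a spread under about 10%. This should be fixed before analysis; it limits interpretation and does not defeat the design.

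**What to change.** Reconcile the Test Meals sentence with Table 1. If the menus stay, replace it with:

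> The four breakfasts are similar in energy and protein; energy density, fat, carbohydrate, fiber, glycemic index and glycemic load differ as shown in Table 1.

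In the SAP paragraph on the crossover models, add:

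> Egg and saturated-fat indicators will be coded +1/2 and −1/2, so that the terms estimate (A+B)/2 − (C+D)/2, (B+D)/2 − (A+C)/2 and (B−A) − (D−C). These are contrasts among the four named breakfasts and will not be attributed to eggs or saturated fat alone.

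Reword the hypotheses to match:
- Hypothesis 5: egg breakfasts (A, B) against cereal breakfasts (C, D), averaged over the two saturated-fat levels, in place of the claim to control for saturated-fat content.
- Hypothesis 6: B and D against A and C.
- Hypothesis 7: whether the egg-minus-cereal difference differs between the two pairs.

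Align the Significance sentence, and the Summary's expectation as far as it is to be read from Part II.

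If the menus stay, the cost is wording only: randomization, sample size, visits and model terms do not change. The downside is a narrower conclusion, about four named breakfasts and not about eggs or saturated fat in isolation.

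### Tables 1 and 2 are inconsistent: the fibre row does not follow from the recipes and the saturated-fat row is implausible given them, so the size and possibly the direction of the dose imbalance are uncertain

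*Combined protocol and SAP*

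**What the plan says.** Section D. Test Meals says the four breakfasts are matched and sets out two tables.

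Table 1 (composition, in the order A, B, C, D):
- "Saturated Fat (g) 5.193 10.893 2.916 10.616"
- "Fat (g) 22.61 24.91 19.55 22"
- "Fiber (g) 10 11.5 7.427 5.667"
- "Weight (g) 328 310 387 352"

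Table 2 (recipes, same order):
- spread: "30g Margarine 15 g Butter 35g Margarine 15 g Butter"
- milk: "120 mL Skim Milk 120 mL 2% milk 200 mL Silk Original Soymilk 200 mL Silk Original Soymilk"
- bread: A and B each have "2 Slices Nature's Own Double Fiber Wheat Bread"; C has one slice of a thin bread and D half a slice of a different bread
- jam: 18 g in A, 15 g in B, 10 g of a sugar-free product in C, none in D

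Eggs are the same in A and B; cereal and soymilk are the same in C and D. No margarine brand and no ingredient-level composition is given.

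Hypothesis 7 states that "the associations mentioned in hypothesis 5 will be moderated by the presence of a high amount of saturated fat in the diet". The SAP enters egg (present or absent), high saturated fat (present or absent) and their interaction in the mixed models.

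**The concern.** Within each pair most ingredients are shared, so the difference between two columns of Table 1 should be explained by the few ingredients that change. It is not. Fibre rises from A to B although nothing that carries fibre increases. The saturated-fat step is larger in the cereal pair, although that swap removes 5 g more margarine, ends with the same 15 g of butter and has no change from skim to 2% milk.

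Saturated fat is one of the two factors that Part II manipulates. If the step differs between the egg pair and the cereal pair, that difference is mixed into the egg-by-saturated-fat interaction. A reader of the results needs to know how large the difference is and which pair has the larger step. The two tables do not give one answer.

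**Working it through.** **Inputs.** All gram figures are from Tables 1 and 2. Food-composition values are assumptions and are marked as such.

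**1. Do the columns line up?** Glycemic load should equal glycemic index × carbohydrate / 100:
- A: 37.48 × 44.37 / 100 = 16.63 (stated 16.63)
- B: 35.98 × 40.45 / 100 = 14.55 (stated 14.55)
- C: 55.54 × 48.741 / 100 = 27.07 (stated 27.07)
- D: 51.52 × 41.8 / 100 = 21.535 (stated 21.53)

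Weight, A to B: the recipe gives −15 g spread and −3 g jam = −18 g; Table 1 gives 310 − 328 = −18 g. Shifted columns are therefore not a likely explanation.

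**2. Fibre, A to B.** Eggs and bread are identical. Milk, butter and margarine are taken to contain no fibre. The only remaining change is 3 g less jam, so B − A must be zero or negative. Table 1: 11.5 − 10 = +1.5 g.

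**3. Saturated fat, general form.** Let b and m be grams of saturated fat per gram of butter and margarine, assumed the same in both pairs. Let t be the extra saturated fat in 120 mL of 2% over skim milk. Let h be D's bread minus C's bread, net of jam.
- Egg pair: B − A = 15b − 30m + t; Table 1: 10.893 − 5.193 = 5.700 g
- Cereal pair: D − C = 15b − 35m + h; Table 1: 10.616 − 2.916 = 7.700 g

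Subtracting cancels the butter: h − t − 5m = 2.000, so **h = 2.0 + 5m + t**.

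Since m and t cannot be negative, h must be at least 2.0 g. The weight row makes D's bread the lighter one: D − C = 352 − 387 = −35 g = −20 g spread − 10 g jam − 5 g bread. All of Breakfast C, including 35 g of margarine, is stated to hold 2.916 g.

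**4. Total fat, same method.** Table 1: B − A = 2.30 g, D − C = 2.45 g, difference 0.15 g. Assume 2% milk adds 2.4 g of fat (2% of about 120 g) over skim, and margarine has f g of fat per gram. D's bread must then hold 0.15 + 2.4 + 5f = 2.55 + 5f g more fat than C's. For assumed f of 0.3 to 0.6, that is 4.05 to 5.55 g. This points the same way.

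**5. What the recipes imply if the breads are similar.** The egg-pair step minus the cereal-pair step is 5m + t − h. Assume t = 1.2 to 1.6 g, m = 0 to 0.12 g/g and h = −0.5 to +0.5 g:
- smallest: 0 + 1.2 − 0.5 = 0.7 g
- largest: 0.6 + 1.6 + 0.5 = 2.7 g

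Table 1 has this quantity at 5.7 − 7.7 = −2.0 g. As an illustration, b = 0.50, m = 0.05, t = 1.5 and h = 0 give B − A = 7.5 − 1.5 + 1.5 = 7.5 g and D − C = 7.5 − 1.75 = 5.75 g.

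**6. Do the high/low labels hold?** Over the same ranges with assumed b = 0.45 to 0.55, the smallest steps are B − A = 6.75 − 3.6 + 1.2 = 4.35 g and D − C = 6.75 − 4.2 − 0.5 = 2.05 g. Both are positive.

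**7. Energy density of C.** 447.48 / 387 = 1.16 against 1.17 stated. The other three columns reproduce.

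**The case against.** The strongest reply is that the saturated-fat argument is not free of assumptions. Table 2 does not say that A and C use the same margarine. The telephone screening form asks about one unbranded margarine, which suggests a single product but does not prove it. Neither bread's composition is given. With two margarines and similar breads, C's margarine would need (15b − 7.7) / 35 g of saturated fat per gram: −0.6% at an assumed b of 0.50 and 1.6% at 0.55. That is impossible or strained, depending on the butter, but it is not a contradiction within the documents. This part of the objection stands. A reader might infer that the saturated-fat row is impossible whatever products are used, or that the tables disagree by at least 2.0 g without any assumption. Neither is supported: with m = 0, t = 0 and h = 0.5 g, for example, the gap is 1.5 g.

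A second reply is that no gram dose enters any model. The SAP codes saturated fat as present or absent, and hypotheses 6 and 7 are worded the same way. Table 1 as printed already shows unequal steps. This also stands. It limits the consequence to describing the doses and interpreting the effects.

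Neither reply explains the fibre row, which depends on no brand. Fibre is not the randomised factor, however, so that error by itself says nothing about the saturated-fat dose.

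**Conclusion.** The two tables are inconsistent and should be reconciled. The fibre conflict between A and B (+1.5 g where the recipes allow at most 0) needs only the premise that milk, butter and margarine contain no fibre. The saturated-fat conflict is probable rather than certain: it rests on the same butter and margarine in both pairs and on a half slice of bread that is not rich in saturated fat.

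Under the assumed milk, margarine and bread values, the egg pair has the larger step by about 0.7 to 2.7 g, where Table 1 gives the cereal pair the larger step by 2.0 g. The direction of the imbalance may therefore be the reverse of what is stated. A reader might take the reversal as established; it depends on composition values that the documents do not contain.

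A reader might also infer that the randomised comparison is invalid or that all Part II hypotheses are affected. The documents do not support that. B stays above A and D above C throughout the assumed ranges, so the high/low coding holds. The consequence is confined to the reported saturated-fat doses and the interpretation of the saturated-fat effect and its interaction with eggs (hypotheses 6 and 7). The documents do not show which table, or which of the four saturated-fat values, is wrong.

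**What to change.** Before the first breakfast is served:
- Recompute every row of Table 1 from the weighed ingredients and labels of the exact products used, naming the margarine and butter.
- Reconcile Tables 1 and 2 so that one recipe reproduces one composition table. Which table is right is for the sponsor to establish.
- State the resulting saturated-fat step in the egg pair and in the cereal pair, and use those figures when reporting hypotheses 6 and 7.
- Correct the energy density of C at the same time.

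The cost is a few hours of recipe calculation and a corrected table, with no added subjects or procedures.
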